6.1.5 Itch Numeric Rating Scale (itch NRS)

At the study Visits 2, 10, 15, 16, and 19 (study weeks 0, 16, 20, 28, and 52) subjects will be asked to assess severity of itching due to psoriasis perceived over past 24 hours at the moment of scoring on

an 11-point scale anchored at 0, representing 'No itch' and 10, representing 'Worst itch imaginable'. ([Appendix VIII](#))

6.1.6 Scalp Itch Numeric Rating Scale (scalp itch NRS) – for subjects with Scalp psoriasis

At the study Visits 2, 10, 15, 16, and 19 (study Weeks 0, 16, 20, 28, and 52) subjects will be asked to assess severity of itching of the scalp due to psoriasis perceived over past 24 hours at the moment of scoring on an 11-point scale anchored at 0, representing 'No scalp itch' and 10, representing 'Worst scalp itch imaginable'. ([Appendix VIII](#))

6.1.7 Health Assessment Questionnaire of disability (HAQ-DI) – for subjects with PsA

The HAQ-DI is a component of American College of Rheumatology (ACR) response Assessments. ACR response assessments will be performed only in subjects who meet the CASPAR Criteria. (see [6.1.16](#)) The ACR components evaluations will be used to calculate the subject's ACR response criteria (ACR20 / 50 / 70)

At the study Visits 2, 10, 15, 16, and 19 (study Weeks 0, 16, 20, 28, and 52) the subject will assess their general disability using the HAQ-DI questionnaire. The HAQ-DI is designed to assess patients' usual abilities using their usual equipment. The time frame for the disability questions is the past week and scoring within each section is from 0 (without any difficulty) to 3 (unable to do). ([Appendix IX](#)) A higher score indicates greater disability.

6.1.8 Patient Global Assessment of Disease Activity (PtGA) – for subjects with PsA

The PtGA is a component of American College of Rheumatology (ACR) response Assessments. ACR response assessments will be performed only in subjects who meet the CASPAR Criteria. (see [6.1.16](#)) The ACR components evaluations will be used to calculate the subject's ACR response criteria (ACR20 / 50 / 70)

At the study visits 2, 10, 15, 16, and 19 (study weeks 0, 16, 20, 28, and 52) the subject will assess their current ('today') global status of PsA using a Visual Analogue Scale (VAS) of 0 to 100. ([Appendix X](#))

6.1.9 Patient Assessment of Pain (PtA-P) – for subjects with PsA

The PtA-P is individual measurement and also a component of American College of Rheumatology (ACR) response Assessments. PtA-P assessments will be performed only in subjects who meet the CASPAR Criteria. (see [6.1.16](#))

At the study visits 2, 10, 15, 16, and 19 (study weeks 0, 16, 20, 28, and 52) the subject will assess their pain due to PsA using a Visual Analogue Scale (VAS). It is a subjective measure of pain. It is a continuous scale, 100 mm in length, anchored by 2 verbal descriptors, one for each symptom extreme ("no pain" and "worst pain imaginable"). Subjects are asked to rate their pain by placing a mark on the line corresponding to their current level of pain. The distance along the line from the "no pain" marker is then measured with a calibrated ruler giving a pain score out of 100. ([Appendix XI](#))

6.1.10 Investigator's Global Assessment (IGA)

At Screening and Baseline, to be eligible for inclusion in the study, subjects must have a definite clinical diagnosis of psoriasis of at least moderate severity (IGA score ≥ 3) as an overall assessment of all psoriatic lesions.

██████████ the Investigator will perform an average assessment of all psoriatic lesions based on erythema, scale, and induration. The static IGA determines psoriasis severity at a single point in time, without taking the baseline disease condition into consideration. The following scale will be used for the IGA:

Table 1: Investigator's Global Assessment (IGA)

Score	Grade	Description
0	[REDACTED]	[REDACTED]
1	[REDACTED]	[REDACTED]
2	[REDACTED]	[REDACTED]
3	[REDACTED]	[REDACTED]
4	[REDACTED]	[REDACTED]

6.1.11 Scalp IGA – for subjects with Scalp psoriasis

Scalp IGA assessments will be performed only in subjects with scalp psoriasis.

At the study Visits 2, 10, 15, 16, and 19 (study Weeks 0, 16, 20, 28, and 52) the Investigator will perform an overall assessment of all scalp psoriasis lesions. The static Scalp IGA determines psoriasis severity at a single point in time, without taking the baseline disease condition into consideration. The following scale will be used for the Scalp IGA:

Table 2: Scalp Investigator's Global Assessment (IGA)

Score	Grade	Description
0	[REDACTED]	[REDACTED]
1	[REDACTED]	[REDACTED]
2	[REDACTED]	[REDACTED]
3	[REDACTED]	[REDACTED]
4	[REDACTED]	[REDACTED]

6.1.12 Palmoplantar Physician Global Assessment (PPPGA) – for subjects with Palmoplantar psoriasis

Palmoplantar Physician Global Assessment (PPPGA) will be performed only in subjects with palmoplantar psoriasis.²²

At the study visits 2, 10, 15, 16, and 19 (study Weeks 0, 16, 20, 28, and 52) the Investigator will perform an overall assessment palmoplantar involvement with a 5-point scale. The static PPPGA determines psoriasis severity at a single point in time, without taking the baseline disease condition into consideration. The following scale will be used for the PPPGA:

Table 3: Palmoplantar Physician Global Assessment (PPPGA)

Score	Grade	Description
0	[REDACTED]	[REDACTED]
1	[REDACTED]	[REDACTED]

Score	Grade	Description
2		
3		
4		

6.1.13 Psoriasis Area and Severity Index (PASI) evaluation

At Screening and baseline, to be eligible for inclusion in the study, subjects must have a definite clinical diagnosis of psoriasis of at least moderate severity (PASI score ≥ 12) as an overall assessment of all psoriatic lesions.

[REDACTED]
[REDACTED] the Investigator will perform psoriasis severity using PASI evaluations. The PASI is a measure of the average redness (erythema), thickness (induration), and scaliness (scaling) of psoriatic skin lesions (each graded on a 0–4 scale), weighted by the area of involvement (head, arms, trunk to groin, and legs to top of buttocks). The PASI produces a numeric score that can range from 0 to 72, with higher PASI scores denoting more severe disease activity. Investigators will perform the efficacy assessments of PASI based on the guidance provided in the training module of the Group for Research and Assessment of Psoriasis and Psoriatic Arthritis (GRAPPA module) ([Appendix III](#))

PASI scores will be used to calculate the subject's PASI response criteria (PASI50, PASI75, PASI90, and PASI100). PASI75 response indicates an improvement in PASI score by at least 75% as compared with a baseline value.

The following PASI scale will be used to evaluate the severity of clinical signs:

Table 4: Psoriasis Area and Severity Index (PASI): Severity

Score	Grade	Severity		
		Redness (Erythema)	Thickness (Induration)	Scaliness (scaling)
0				
1				
2				
3				
4				

The total PASI score is calculated as follows (to be performed programmatically by DM):

Area	PASI Clinical Signs Severity Score			Total Severity Score	Extent*	Weighting factor	Total
	Redness	Thickness	Scaliness				
Head and neck	+	+	=	x	x	0.1	=
Arms	+	+	=	x	x	0.2	=
Trunk	+	+	=	x	x	0.3	=
Legs	+	+	=	x	x	0.4	=
Total PASI Score (sum of above)							=

*the Extent of area involving psoriasis is assigned according to the table below:

Extent	% affected
0	0 (noninvolvement)
1	< 10%
2	10 – 29%
3	30 – 49%
4	50 – 69%
5	70 – 89%
6	90 – 100%

6.1.14 Body Surface Area (BSA)

At Screening and Baseline, to be eligible for inclusion in the study, Subjects must have a definite clinical diagnosis of psoriasis of at least moderate severity (BSA involvement $\geq 10\%$) as an overall assessment of all psoriatic lesions. The handprint method will be used to estimate % BSA.

the Investigator will assess % BSA affected with psoriasis using instructions in [Appendix II](#).

6.1.15 Modified Nail Psoriasis Severity Index (mNAPSI) – *for subjects with Nail psoriasis*

Modified Nail Psoriasis Severity Index assessments will be performed only in subjects with nail psoriasis. ²³

the Investigator will perform an assessment of each affected finger nail abnormality. The mNAPSI produces a numeric score that can range from 0 to 130 (maximum of 13 for each fingernail), with higher mNAPSI scores denoting more severe disease activity. The following scale will be used for the mNAPSI:

Table 5: Modified Nail Psoriasis Severity Index (mNAPSI)

Nail abnormality	Score and Description
Onycholysis and oil-drop (salmon patch) dyschromia	0 = No onycholysis or oil drop dyschromia present 1 = 1–10% of the nail has onycholysis or oil-drop dyschromia 2 = 11–30% of the nail has onycholysis or oil-drop dyschromia 3 = > 30% of the nail has onycholysis or oil-drop dyschromia
Pitting	0 = No pitting 1 = 1–10 pits 2 = 11–49 pits 3 = ≥ 50 pits
Nail plate crumbling	0 = No crumbling 1 = 1–25% of the nail has crumbling 2 = 26–50% of the nail has crumbling 3 = > 50% of the nail has crumbling
Leukonychia	0 = Absent 1 = Present
Splinter hemorrhages	0 = Absent

Nail abnormality	Score and Description
	1 = Present
Hyperkeratosis	0 = Absent 1 = Present
Red spots in the lunula	0 = Absent 1 = Present

6.1.16 CASPAR Classification Criteria for Psoriatic Arthritis

All subjects with a medical history of PsA reported at the screening or baseline will be assessed to establish if there is a diagnosis of PsA per the Classification of Psoriatic Arthritis (CASPAR) criteria.¹² The diagnosis of PsA will be done by a rheumatologist or an orthopedist, or a qualified trained designee (not applicable at sites where an independent assessor experienced in performing joint assessments is not available). According to CASPAR, the establishment of the diagnosis of PsA requires the presence of inflammatory joint disease (peripheral, axial or enthesitis) with at least three points from the following features: evidence of skin psoriasis (current psoriasis was assigned a score of 2, while history of psoriasis or familial history of psoriasis were assigned a score of 1 each, as were all the other features), psoriatic nail dystrophy, rheumatoid factor negativity, dactylitis, and characteristic radiological evidence

Table 6: CASPAR Classification Criteria for Psoriatic Arthritis

Required criterion (must be Yes)	

 inflammatory joint disease (peripheral, axial or enthesitis) 	
and additional categories (must have 3 points or more)	
1. Evidence of skin psoriasis (select the option that assigns the most points, (e.g., if both current psoriasis and family history, select current psoriasis))	

 Current personal history family history 	2 points 1 point 1 point
2. Psoriatic nail dystrophy (onycholysis, pitting, and hyperkeratosis)	1 point
3. Negative test results for rheumatoid factor	1 point
4. Dactylitis	

 current inflammation of an entire digit history of dactylitis recorded by a rheumatologist 	1 point 1 point
5. Radiological evidence of juxta-articular new bone formation (ill-defined ossification near joint margins (but excluding osteophyte formation) on plain radiograph of hands and feet)	1 point

6.1.17 Tender and Swollen Joint count – for subjects with PsA

The tender and swollen joint count is a component of American College of Rheumatology (ACR) response Assessments. ACR response assessments will be performed only in subjects who meet the CASPAR Criteria. (See [6.1.16](#)) The ACR components evaluations will be used to calculate the subject's ACR response criteria (ACR20 / 50 / 70)

At the study Visits 2, 10, 15, 16, and 19 (study Weeks 0, 16, 20, 28, and 52) tender and swollen joint counts will be performed by an independent Investigator rheumatologist or qualified trained designee.

Joint count includes the majority of joints affected in PsA, 68 for tenderness and 66 for swelling. It includes the temporomandibular, sternoclavicular, acromioclavicular, shoulder, elbow, wrist (including the carpometacarpal and intercarpal joints as 1 unit), metacarpophalangeal (MCP), proximal interphalangeal (PIP), DIP, hip, knee, talotibial, midtarsal (including subtalar), metatarsophalangeal, and interphalangeal joints of the toes (proximal and distal joints of each toe is counted as 1 unit) for assessment of tenderness. The 66 joints to be examined for swelling are the same as those of tenderness, except the hip joints are not included. The assessments will be performed using instructions in Appendix XII and tender and swollen joint numbers will be recorded in a Joint Count Scoring Sheet.

6.1.18 Physician Global Assessment of Disease Activity (PGA) – *for subjects with PsA*

The PGA is a component of American College of Rheumatology (ACR) response assessments. ACR response assessments will be performed only in subjects who meet the CASPAR Criteria. (see [6.1.16](#)) The ACR components evaluations will be used to calculate the subject's ACR response criteria (ACR20 / 50 / 70)

At the study Visits 2, 10, 15, 16, and 19 (study Weeks 0, 16, 20, 28, and 52) the status of the subject's PsA will be assessed by an independent Investigator rheumatologist or qualified trained designee using a VAS of 0 to 100. The subject will be assessed according to how their current arthritis is. The VAS will be anchored with verbal descriptors of "No Disease Activity" to "Maximum Disease Activity" (Appendix XIII)

6.1.19 American College of Rheumatology (ACR) response Assessments

ACR response assessments will be performed only in subjects who meet the CASPAR Criteria. (See [6.1.16](#)) The ACR components evaluations will be used to calculate the subject's ACR response criteria (ACR20 / 50 / 70). ACR20 response indicates a decrease of at least 20% in both the number of tender and swollen joint counts, as well as a 20% improvement in at least three of five scores of individual components:

1. Health Assessment Questionnaire of disability (HAQ-DI).
2. Patient global assessment of disease activity (PtGA) on VAS of 0 to 100.
3. Patient assessment of pain (PtA-P) on VAS of 0 to 100.
4. Physician global assessment of disease activity (PGA) on a VAS of 0 to 100.
5. C-reactive protein (CRP) level, mg/dl.

ACR50 and ACR70 are the same measurements with improvement levels defined as 50% and 70% respectively.

6.2 Pharmacokinetics

Blood (approximately 4 ml) will be collected for each PK sample. Pre-dose (trough) PK samples (within one hour before dosing) will be collected at study Visits 10, 15, 16, and 19 (study Weeks 16, 20, 28, and 52).

In addition, PK sample will be collected, if possible, approximately 1 hour within the onset of an adverse event related to bradycardia during on-site visits with dose titration monitoring.

PK samples collected only from the active treatment groups will be analysed in an unblinded manner.

The plasma samples collected at above-mentioned time points may be used for assay of metabolites, if required.

[REDACTED]

6.3 Pharmacodynamic (PD) biomarkers

[REDACTED] a blood sample will be collected for testing of:

- Cytokines in plasma/serum: [REDACTED]
- Cell types in blood:
 - [REDACTED]
 - [REDACTED]
 - [REDACTED]
 - [REDACTED]
 - [REDACTED]
 - [REDACTED]

Additional biomarkers may be included during the study.

[REDACTED]

Subjects who are withdrawn permanently from study drug but remain in the study should not have any more PD biomarker samples taken.

6.4 Photography (Optional)

Photography is an optional procedure in the study. Only at selected centers that have the ability and expertise taking digital photographs, the subjects will be asked if they want to participate in the photography portion of this study. The subject must indicate in the informed consent form if he/she consents to photography in the study. At the study Visits 2, 10, and 19 (study Weeks 0, 16, and 52), photography will be performed of the overall body. Photographs will be used for visual evaluation only and will not be included in any analyses. Details of photographic evaluation including handling, labeling and transfer of photographs will be included in a photography manual.

7 STUDY VISITS

At study visits the efficacy assessments have to be performed in the following order:

- the patient-rated questionnaires like DLQI, itch NRS, PtA-P, HAQ-DI, must be completed prior to the Investigator assessments
- Investigator Global assessment (IGA) for Psoriasis, Scalp only IGA, PPPGA, PGA for Psoriatic arthritis must be completed prior to other efficacy assessments
- PASI, BSA, mNAPSI, remaining components of ACR assessment in PsA subjects.

ACR20 assessments will be performed by an Independent Joint Assessor (independent Investigator rheumatologist or an orthopedist, or a qualified trained designee). ACR20 assessments are not applicable at sites where an independent assessor experienced in performing joint assessments is not available. The subject and his/her caregiver will be instructed to take care not to discuss aspects of the subject's treatment with the Investigator or the joint assessor.

The Central Independent MM will inform the Safety Assessor at the site if alert values are met for ALC and if repeat tests or dose interruption are needed because of laboratory abnormalities or because of findings from dose titration monitoring.

If necessary due to the COVID-19 pandemic, Visits 17 and 18 may have assessments done at home or remote visit. Remote visits must be discussed and consulted with the CRO's and the Sponsor's medical monitor before planning. Scheduled blood collection (for these visits only) may be waived if the individual subjects have not had clinically significant changes or undesired trend in laboratory or chemistry values

prior to Visit 15. Remote assessments or delayed Visits 17 or 18 will be recorded in the source documents and noted as a minor protocol deviation.

Changes in study visit schedules, missed visits, or subject discontinuations may lead to missing information (e.g., for protocol-specified procedures). It is important to capture *specific* information in the case report form that explains the basis of the missing data, including the relationship to COVID-19, for missing protocol-specified information (e.g., from missed study visits or study discontinuations due to COVID-19).

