8. A query for PML (progressive multifocal leukoencephalopathy) will be performed (See Section 5.10)
9. A query for PRES (Posterior reversible encephalopathy syndrome) will be performed (See Section 5.11)
10. The Subject's body weight will be measured while the Subject is lightly clothed (e.g., no coat or shoes)
11. The Subject's diary provided at the previous visit will be collected and reviewed.
12. The returned study drugs will be counted
13. The use of concomitant medications since the previous study visit will be documented and assessed. (See Section 5.8)
14. A urinalysis dipstick will be performed and evaluated at a site (See Section 5.5)
15. A blood sample will be collected for Hematology, Lipid Profile, Chemistry, and Coagulation profile (See Section 5.5)
16. A blood sample will be collected for PD biomarkers sample (See Section 6.3)
17. A blood sample will be collected within one hour before dosing for PK testing (See Section 6.2)
18. A blood sample will be collected for C-reactive protein (CRP) – (See Section 5.5)
19. Independent Safety Assessor review:
 - Safety Lab Alerts
 - [REDACTED]
 - As available
 - i. Lab results
 - ii. Exam results
20. Study drug administration in a clinic before 12 noon (See Section 8.5)
21. [REDACTED]
[REDACTED]
[REDACTED]
22. A general safety review before discharge
23. On-site Visit 14 (Study Day 134 ±1 Day) will be scheduled and the Subject will be instructed to bring the Study Product (used, unused, and partially used packs), and Subject diary with him or her to this visit.
24. [REDACTED]
[REDACTED]
[REDACTED]

■ [REDACTED]
■ [REDACTED]
■ [REDACTED]

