7.1.7 On-site Visit 14: Visit [REDACTED]

The following procedures will be performed by an independent safety team at Visit 14:

1. The occurrence of all AEs & AESIs will be assessed and documented following the procedures in Sections 5.9, 10.1, and 10.3.
2. A query for PML (progressive multifocal leukoencephalopathy) will be performed (See Section 5.10)
3. A query for PRES (Posterior reversible encephalopathy syndrome) will be performed (See Section 5.11)
4. The Subject's diary provided at the previous visit will be collected and reviewed.
5. The returned study drugs will be counted
6. The use of concomitant medications since the previous study visit will be documented and assessed. (See Section 5.8)
7. Vital signs (blood pressure, pulse, respiratory rate and oral body temperature) will be documented. Subjects must remain in a seated or supine position for at least 5 minutes before vital signs are obtained. (See Section 5.3)
8. A blood sample will be collected for Hematology (See Section 5.5)
9. Independent Safety Assessor review:
 - Safety Lab Alerts
 - [REDACTED]
 - As available
 - i. Lab results
 - ii. Exam results
10. The following will be dispensed during Visit 14:
 - The study drug assembled for Visit 14
 - A diary card with instructions and to record the study drug use, health changes and concomitant medication
11. A general safety review before discharge
12. [REDACTED]
[REDACTED]
[REDACTED]

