10. Vital signs (blood pressure, pulse, respiratory rate and oral body temperature) will be documented. Subjects must remain in a seated or supine position for at least 5 minutes before vital signs are obtained. (See Section 5.3)
11. A blood sample(s) will be collected for Hematology and Chemistry (See Section 5.5)
12. A blood sample will be collected within one hour before dosing for PK testing (See Section 6.2)
13. Study drug administration in a clinic before 12 noon (See Section 8.5)
14. Independent Safety Assessor review:
 - Safety Lab Alerts
 - [REDACTED]
 - As available
 - i. Lab results
 - ii. Exam results

The following procedures will be performed prior a subject discharged from a clinic:

15. The following will be dispensed during Visit 15:

- UPT to be performed at home at week 24 – *for female Subjects of childbearing potential* (see section 5.4)
- The study drug assembled for Visit 15
- A diary card with instructions and to record the study drug use, health changes and concomitant medication

16. A general safety review before discharge

17. [REDACTED]

18. A phone call will be scheduled at the study week 24 to collect information on the study drug use, UPT, health changes and concomitant medication.

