10. A blood sample(s) will be collected for Hematology, Chemistry, and Coagulation profile (See Section 5.5)
11. A blood sample will be collected for PD biomarkers sample (See Section 6.3)
12. A blood sample will be collected within one hour before dosing for PK testing (See Section 6.2)
13. A blood sample will be collected for C-reactive protein (CRP) – (See Section 5.5)
14. Vital signs (blood pressure, pulse, respiratory rate and oral body temperature) will be documented. Subjects must remain in a seated or supine position for at least 5 minutes before vital signs are obtained. (See Section 5.3)

If Subject eligible to continue the study drug dosing based on PASI response ≥75

15. Independent Safety Assessor review:
 - Safety Lab Alerts
 - [REDACTED]
 - As available
 - i. Lab results
 - ii. Exam results
16. Study drug administration in a clinic before 12 noon (See Section 8.5)
17. The following will be dispensed during Visit 16:
 - The study drug assembled for Visit 16
 - A diary card with instructions and to record the study drug use, health changes and concomitant medication
18. A general safety review before discharge
19. [REDACTED]
[REDACTED]
[REDACTED]

If Subject discontinue from the study drug dosing based on PASI response <75 (the visit is to be reported as End of Treatment)

15. Independent Safety Assessor review:
 - Safety Lab Alerts
 - [REDACTED]
 - As available
 - i. Lab results
 - ii. Exam results
16. The following will be dispensed during Visit 16:
 - a. A diary card with instructions and to record health changes and concomitant medication
17. A general safety review before discharge

Confidential

18. [REDACTED]
[REDACTED]

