## 3. STUDY OVERVIEW

### 3.1 Study Design

Subjects in this randomized, double-blind, placebo controlled, parallel-group, multiple-center study will be assigned to treatment with the investigational products or placebo control according to a randomization scheme and [REDACTED] schedule.

- **Part I:** 16 weeks; Subjects will be randomized to placebo, Low dose ( [REDACTED] Intermediate dose ( [REDACTED] or High dose ( [REDACTED] of SCD-044 in [REDACTED] to assess primary and secondary endpoints at Week 16
- [REDACTED]  
[REDACTED]  
[REDACTED]  
[REDACTED]  
[REDACTED]  
[REDACTED]  
[REDACTED]

- [REDACTED]
- [REDACTED] response of [REDACTED] at Week 28 will
- [REDACTED]

[REDACTED]

Clinical Evaluations will be performed at:

- [REDACTED]
- [REDACTED]

Phone or in person contacts may be scheduled [REDACTED]

[REDACTED] to collect information on concomitant medication, compliance with the study drug use, health changes (AEs & AESI), queries for PML and PRES and to provide instructions.

[REDACTED]  
[REDACTED]

Subjects will be admitted into the study after informed consent has been obtained. An Unscheduled Visit is allowed at any time, for any reason, if in the Principal Investigator's opinion it is warranted. If a Subject is discontinued from the study during an Unscheduled Visit, the Unscheduled Visit will be referred to as an Early Discontinuation Visit and all procedures scheduled for Early Discontinuation will be performed. If the Unscheduled Visit is not an Early Discontinuation Visit (i.e., the Subject will continue to take part in the study), then all procedures scheduled for that Unscheduled Visit will be performed. Subjects who are discontinued early from the study must attend the Follow-up visit 4 weeks after the date of Early Discontinuation.

If necessary due to the coronavirus disease-2019 (COVID-19) pandemic, Visits 17, and 18 may have assessments done at home or remote visit. Remote visits must be discussed and

consulted with the Contract Research Organization's (CRO) and the Sponsor's Medical Monitor (MM) before planning. Scheduled blood collection (for these visits only) may be waived if the individual subjects have not had a clinically significant changes or undesired trend in lab or chemistry values prior to Visit 15. Subjects that have remote assessments or delayed Visits 17, or 18 will be recorded in the electronic case report form (eCRF) and noted as a minor protocol deviation.

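### The waiver of the hematology draw at remote Visits 17 and 18 looks only at results before Week 20, so the Week 20 and Week 28 panels already collected do not count

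*Protocol*

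**What the plan says.** Protocol section 7 allows Visits 17 and 18 to be held remotely because of COVID-19, after discussion with the CRO's and the sponsor's medical monitors. The scheduled blood draw at those two visits may then be waived if the subject has had no clinically significant change or undesired trend in laboratory values up to a stated point. The end of that condition and the start of the next sentence read "prior to Visit 15. Remote assessments or delayed Visits 17 or 18 will be recorded in the source documents". SAP section 3.1 sets the same limit: "clinically significant changes or undesired trend in lab or chemistry values prior to Visit 15". Protocol section 3 has a parallel paragraph, but its visit numbers and cut-off are redacted.

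The laboratory schedule is in Protocol section 5.5 and the visit lists in section 7.1:

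- Visit 10 is Week 16, Visit 15 is Week 20, Visit 16 is Week 28 and Visit 19 is Week 52.
- Visit 14 draws hematology only. Section 7.1.6 fixes its date: "On-site Visit 14 (Study Day 134 ±1 Day) will be scheduled".
- Visit 15 draws hematology and chemistry. Visit 16 draws hematology, chemistry and coagulation.
- Visits 17 and 18 draw hematology only.

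Treatment can change at Week 16 (Protocol section 3): placebo subjects are re-randomized to active doses, and some low- and intermediate-dose subjects move to the high dose. Dosing beyond Week 28 depends on response. Section 7.1.9 introduces the continuing branch with "If Subject eligible to continue the study drug dosing based on PASI response ≥75".

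**The concern.** A rule that lets a safety sample be skipped because earlier results were clean should look at the latest results. This one stops before Week 20, although two later panels are in hand before the first waivable visit.

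The cut-off fits this design badly. For a former placebo subject, every result up to Week 16 is off drug. The SAP recognizes the break: sections 6.1 and 6.11.2 use a new Part II baseline for laboratory analyses in subjects who switch. Yet the waiver rests almost wholly on results from before the switch. One later hematology value cannot show a trend on the new regimen, and the Week 20 and Week 28 values that could show one are excluded.

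The sample at stake is the one that matters for this drug. SCD-044 lowers lymphocyte counts (Protocol section 1), infection is a listed class risk (section 4.6), and serious infections and PML are events of special interest (section 5.9). A subject whose count first drifts the wrong way at Week 20 or 28, without reaching an alert value, meets the written condition and can miss the next draw.

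**Working it through.** The plan gives no figure to reproduce. The check maps visits to days and compares the look-back window with the samples collected.

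**Day numbering.** Week 52 is Day 365 and Week 56 is Day 393, so Week *w* = Day 7*w* + 1 (7 × 52 + 1 = 365; 7 × 56 + 1 = 393).

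- Week 16 (Visit 10): 7 × 16 + 1 = Day 113
- Visit 14: Day 134 (section 7.1.6)
- Week 20 (Visit 15): 7 × 20 + 1 = Day 141
- Week 28 (Visit 16): 7 × 28 + 1 = Day 197

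**What counts after a Week 16 change (visible all-subject schedule).**

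| Visit | Day | Samples | Counts toward the waiver? |
|---|---|---|---|
| 14 | 134 | Hematology | Yes |
| 15 | 141 | Hematology, chemistry | No |
| 16 | 197 | Hematology, chemistry, coagulation | No |

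- Last result that counts: 134 − 113 = 21 days after the change. This takes Visit 10 at its nominal day; its window is redacted, and Visit 14 has ±1 day.
- Last result collected before Visit 17: 197 − 113 = 84 days after the change.
- Follow-up left out: 197 − 134 = 63 days.
- Hematology samples that count: 1 of 3. If the unseen Visits 11 to 13 on the higher-risk schedule also draw hematology (an assumption), up to 4 of 6 count, still none from Week 20 or later.
- Chemistry: the last result that counts is Week 16, so in this schedule no chemistry on a changed regimen counts.

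**Age of the newest result that the condition names.** The weeks of Visits 17 and 18 are redacted. Section 8.6 places phone calls at Weeks 24, 36, 44 and 48 where visits are more than 4 weeks apart. Visit 17 supplies a home pregnancy test for Week 36, and Visit 18 supplies tests for Weeks 44 and 48. This points to Visit 17 at Week 32 (7 × 32 + 1 = Day 225) and Visit 18 at Week 40 (7 × 40 + 1 = Day 281).

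| Waiver decision at | As written | With the look-back extended |
|---|---|---|
| Visit 17 | 225 − 134 = 91 days | 225 − 197 = 28 days |
| Visit 18, Visit 17 drawn | 281 − 134 = 147 days | 281 − 225 = 56 days |
| Visit 18, Visit 17 waived | 281 − 134 = 147 days | 281 − 197 = 84 days |

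These ages depend on the inferred weeks. The main point needs only that both visits fall after Week 28.

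**The case against.** The strongest reply is that the Week 20 and Week 28 panels are left out of one written precondition, not out of safety review. The independent safety assessor sees laboratory alerts and available results at Visits 15 to 18. The central independent medical monitor tells the site "if alert values are met for ALC and if repeat tests or dose interruption are needed". Remote visits need prior consultation with two medical monitors, and meeting the condition obliges nobody to skip a draw. All of this stands, and it limits the risk. It does not repair the criterion: alerts catch threshold breaches, whereas the waiver has its own test, which includes undesired trends and looks at the wrong window.

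A second reply is that the ages in the working describe the newest result named in the condition, not the newest available. The Week 28 sample is taken either way, and changing the cut-off adds no earlier sample. That is correct. If both visits are waived there is no scheduled hematology from Week 28 to Week 52, but that gap comes from the waiver itself, not from the cut-off.

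Third, the affected group is narrow: a COVID-19 remote visit, continuation past Week 28, a first undesired trend at Week 20 or 28 with no alert, and a decision to waive. Subjects who did not switch have several earlier hematology results on their assigned dose. Lymphocyte reduction is also the intended effect, so what counts as undesired is a judgement. Finally, redacted text on laboratory follow-up, discontinuation and management may contain other safeguards. These points stand and argue for a low rating. None shows that the stated cut-off is right.

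**Conclusion.** The concern holds, as a minor point. Protocol section 7 and SAP section 3.1 state a look-back window that ends too early, and no visible text extends it. In the visible schedule, a subject whose treatment changed at Week 16 is judged on one post-change hematology result, nominally 21 days in, while 63 further days of collected follow-up are disregarded. The wording is certain. The consequence is less so, because other safeguards exist and some relevant text is redacted. The number of subjects affected cannot be estimated from the documents. No chemistry draw is lost at Visits 17 and 18, since none is scheduled there, and no efficacy analysis changes.

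**What to change.** In Protocol section 7 and SAP section 3.1, replace the Visit 15 cut-off with *at any visit up to the most recent available result before the visit being waived*. That brings Visits 15 and 16 into the Visit 17 decision, and also Visit 17, if drawn, into the Visit 18 decision. Make the same change in Protocol section 3 if its redacted cut-off matches. The consultation with the medical monitors, and the judgement of what is a significant change or undesired trend, can stay as they are.

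The cost is one phrase in each document, using data already collected. The downside is that a few more remote-visit subjects would not qualify for the waiver and would need a blood draw.
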